responders involved in the opioid and heroin epidemic (law enforcement, firefighters, and emergency medical system personnel) compared to baseline measures and reduced stress as measured by salivary cortisol.

Specific aim #2: Determine delivery and acceptability among first responders in Appalachia. MBRT is relatively novel in this population and to our knowledge has never been applied to a broader first responder community outside law enforcement and not to our knowledge in Appalachia.

Specific aim #3: Evaluate the delivery of MBRT in an intensive 2.5 day setting with follow up remotely with an online communication method such as Skype, FaceTime, or Zoom.

Hypotheses: We hypothesize the following based on previous research:

- 1. MBRT will improve self-reported measures over the 2.5-day intensive intervention with a remote, virtual booster intervention 4 weeks after the 2.5-day initial intervention relative to baseline: a) Mindfulness and resilience, b) Physical and mental health, c) Stress and burnout, d) Emotional functioning, and e) Family functioning, f) Sense-making and decision-making.
- Pre- to post-MBRT changes in mindfulness, physical health, mental health, and stress would predict post-MBRT salivary cortisol, while controlling for pre-MBRT salivary cortisol

Design

1. Fully describe all procedures to be performed in sequential order in outline format.

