The impetus of the proposed research project came from meetings of the Great Rivers Harm Reduction Coalition, which includes public health and first responders from Cabell, Kanawha, and Putnam Counties. It was clear from discussions about the breadth and depth of the opioid and heroin epidemic that first responders are an overlooked vulnerable population in this public health crisis. Law enforcement, fire, and EMS personnel stated they need a means to cope with the daily onslaught of overdoses and interdiction efforts in addition to their daily calls and would be amenable to a resilience-building and stress-reducing intervention involving research into the effectiveness of the intervention. Subjects for the proposed research would be first responders from the three-county area, but primarily from the cities of Charleston and Huntington. Subjects will be recruited from volunteers targeting leadership and thought leaders at the frontline. Each 2.5-day intensive immersion into MBRT would be coordinated with each agency to ensure maximum participation without disrupting work schedules. Up to 35 participants will participate in each cohort. This study aims to recruit 2 cohorts from the pool of first responders in the Cabell, Kanawha, and Putnam Counties area for a minimum of 50 participants. Self-report measures will be conducted at time 0 (before the intervention), time 1 (after the 2.5-day intensive training), time 2 (4 weeks after the 2.5-day intensive training and after the week 4 remote/virtual booster training) and at time 3 (90 days after the initial intensive training). The self-report questionnaires will include the Five Facet Mindfulness Questionnaire (FFMQ), a 39item questionnaire assessing individuals' daily tendency to be mindful.² The Mindfulness Process Questionnaire (MPQ) is a 7 question self-report measure that assesses the degree how mindfulness is intentionally practiced or attempted and the ability to bring compassionate awareness to the present moment after observing the attention has drifted off or become

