judgmental.³ The Brief Resilience Scale is a 6-item scale designed to assess the ability to recover from stress using a 5 point Likert scale.⁴ To measure health outcomes, the Patient Reported Outcomes Measurement Information System (PROMIS®) designed to improve selfreported In this study, we plan to use short form versions of several PROMIS domains to assess health outcomes. The Global Health Short-Form is a 10-item instrument representing multiple domains that can be scored into a Global Physical Health (GPH) component and Global Mental Health (GMH) component. Additionally, we assessed Anger (8 items), Fatigue (4 items), Sleep Disturbance (4 items), and Pain Interference (4 items). All items are rated on a 5-point Likert-type scale using various endpoints.⁵ Stress and burnout will be measured with the 4-item Perceived Stress Scale-4 (PSS-4) to assess perceived stress in life situations.⁶ The Police Stress Questionnaire (PSQ) is a 40-item questionnaire consisting of two subscales measuring operational stressors (20 job content items) and organizational stressors (20 job context items) on a seven-point Likert-type scale, ranging from 1 (no stress at all) to 7 (a lot of stress), and higher scores indicate greater stress. Nearly all the questions could be applicable to all first responder groups. ⁷ The Oldenburg Burnout Inventory (OLBI) is a 16-item measure of burnout with two dimensions: exhaustion and disengagement.8 The Emotional Intelligence Scale (EIS; Schutte et al. 1998) is a 33-item scale of emotional intelligence. Items are rated on a 5-point Likert scale ranging from 1 (strongly disagree) to 5 (strongly agree), and three items are reverse scored. All items are summed to create a total score, and higher scores indicate greater emotional intelligence. 9 The Difficulties in Emotion Regulation Scale (DERS) is a 36-item measure that assesses clinically relevant difficulties in emotion regulation. Items are scored on six scales: lack of emotional awareness (6 items), lack of emotional clarity (5 items), difficulties controlling impulsive behaviors when distressed (6 items), difficulties engaging in goal-directed behavior when distressed (5 items), non-acceptance of negative emotional responses (6 items), and limited access to effective emotion regulation strategies (8 items).10 Family functioning will be measured through the Family Assessment Device (FAD), a 60-item measure.11 The FAD consists of six subscales and a seventh subscale (general family functioning: GFF) incorporates items from the six subscales. In this study we plan to use the 12-item GFF scale, which can be used as an indicator reflecting global family functioning. 12 Salivary cortisol is a biologic marker for stress and is a measure of the hypothalamic-pituitary-adrenal axis (HPA axis). One of the characteristics of the HPA axis is the strong circadian rhythm and the cortisol awakening response (CAR). Salivary cortisol levels are highest in the morning after awakening, and decline throughout the day and lowest around midnight, to rise again in the early morning hours. A distinct characteristic of the HPA axis is the cortisol awakening response (CAR). 13 The CAR is characterized by a sharp rise (between 50 and 75%) of cortisol levels within the first 30 minutes after awakening. 14 Repeated measurement of free cortisol levels within the 60 minutes after awakening in the morning is considered a stable and reliable biological marker of adrenocortical activity.15 We plan to collect approximately 2-3 ml of saliva at 0, 30, and 45 minutes after awakening in the morning at times 0,1,2, and 3 as described above. To examine changes in our measures during the course of MBRT, we plan to use a multilevel modeling approach with restricted maximum likelihood estimation (REML) to examine linear change over time as a fixed effect. We used REML because our data collection resulted in varying sample sizes for our measures, allowing for more accurate estimates with small sample sizes and missing data that are missing at random or completely at random ^{16,17} To test whether changes in mindfulness, emotional intelligence, and difficulties with emotion regulation (i.e., process variables) preceded changes in mental health, physical health, stress, pain interference, anger, fatigue, sleep disturbance, burnout, resilience, and family functioning (i.e., outcome variables), using the

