
multilevel modeling approach, we plan to examine which variables significantly change from time 0 to time 1, from time 1 to time 2, from time 2 to time 3, and from time 0 to time 2 and time 3. To analyze the CAR, plan to use multilevel modeling with REML examining the main effects of phase of measurement (pre, post as above) and time after waking (0, 30, 45 minutes), as well as the interaction between the main effects. We also plan to investigate the association between the cortisol response patterns and change in mindfulness (FFMQ), stress (PSS-4), physical health, and mental health. For that purpose, we plan to analyze the area under the curve with respect to increase (AUCI) to analyze the linear relationship between each independent variable and cortisol awakening levels. Cortisol levels will be transformed into a single value by calculating the AUCI for each assessment day (1 pre and 1 post). These variables will be used in a hierarchical linear regression with pre-AUCI entered in step 1, and change in stress, physical health, mental health, and mindfulness entered in step 2, to predict post-AUCI. Alpha will be set at .05 for all analyses. The PI will be responsible for recruitment of subjects and coordinating with researchers and staff at WVU for analysis and will help oversee the implementation of the intervention. The co-PI will also assist with overseeing the intervention as well as scheduling follow-up, particularly in the Huntington community and will assist in analysis and in evaluation of difficulties. Such difficulties may include scheduling difficulties for follow-up after the intensive intervention, subject drop-out, and sustaining local resources to assist the subjects.

2. Discuss probability of group assignment to experimental and control groups.

Participants will serve as their own controls so they will participate in both the control group and the interventional group.

3. Inclusionary Criteria

Participants must meet the following inclusionary criteria to be eligible for the study: Be employed as a law enforcement official, firefighter, or emergency medical services technician or supervisor from Cabell, Kanawha, or Putnam Counties.

4. Exclusionary Criteria

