The Mindfulness Process Questionnaire (MPQ) is a 7 question self-report measure that assesses the degree how mindfulness is intentionally practiced or attempted and the ability to bring compassionate awareness to the present moment after observing the attention has drifted off or become judgmental.³

c. How frequently will data be monitored?

Self-report measures will be conducted at time 0 (before the intervention), time 1 (after the 2.5-day intensive training), time 2 (4 weeks after the 2.5-day intensive training and after the week 4 remote/virtual booster training) and at time 3 (90 days after the initial intensive training). Data will be monitored during each of these times.

d. What analyses will be performed on the data?

Data completeness will be assessed for missing data field at all times. The analysis after time 1 and each subsequent time will include changes in mindfulness, emotional intelligence, and difficulties with emotion regulation (i.e., process variables) preceded changes in mental health, physical health, stress, pain interference, anger, fatigue, sleep disturbance, burnout, resilience, and family functioning (i.e., outcome variables), using the multilevel modeling approach, we plan to examine which variables significantly change from time 0 to time 1, from time 1 to time 2, from time 2 to time 3, and from time 0 to time 2 and time 3.

Aim 1 Analyses

Descriptive statistics such as frequencies and proportions will be computed for each of the quantitative measures described in the sections above. To examine changes in our measures during the course of MBRT, we plan to use a multilevel

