modeling approach with restricted maximum likelihood estimation (REML) to examine linear change over time as a fixed effect. We used REML because our data collection resulted in varying sample sizes for our measures, allowing for more accurate estimates with small sample sizes and missing data that are missing at random or completely at random ^{16,17} To test whether changes in mindfulness, emotional intelligence, and difficulties with emotion regulation (i.e., process variables) preceded changes in mental health, physical health, stress, pain interference, anger, fatigue, sleep disturbance, burnout, resilience, and family functioning (i.e., outcome variables), using the multilevel modeling approach, we plan to examine which variables significantly change from time 0 to time 1, from time 1 to time 2, from time 2 to time 3, and from time 0 to time 2 and time 3.

Aim 2 Analyses

To analyze the CAR, plan to use multilevel modeling with REML examining the main effects of phase of measurement (pre, post as above) and time after waking (0, 30, 45 minutes), as well as the interaction between the main effects. We also plan to investigate the association between the cortisol response patterns and change in mindfulness (FFMQ), stress (PSS-4), physical health, and mental health. For that purpose, we plan to analyze the area under the curve with respect to increase (AUCI) to analyze the linear relationship between each independent variable and cortisol awakening levels. Cortisol levels will be transformed into a single value by calculating the AUCI for each assessment day (1 pre and 1 post). These variables will be used in a hierarchical linear regression with pre-AUCI entered in step 1, and change in stress, physical health, mental health, and mindfulness entered in step 2, to predict post-AUCI. Alpha will be set at .05 for all analyses.

Process Evaluation

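### The plan announces a test of whether process changes came before outcome changes, but listing which variables change significantly in each interval does not test order

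*Combined protocol and SAP*

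**What the plan says.** Under Design item 6d, Aim 1 Analyses, the plan sets out an inferential purpose: "To test whether changes in mindfulness, emotional intelligence, and difficulties with emotion regulation (i.e., process variables) preceded changes in mental health" and nine other outcomes. The method follows in the same sentence: using a "multilevel modeling approach, we plan to examine which variables significantly change from time 0 to time 1, from time 1 to time 2", then over times 2–3, 0–2 and 0–3. Design item 1 says the same thing in the same terms. The opening paragraph of item 6d has a version that no longer parses: it begins "The analysis after time 1 and each subsequent time will include changes in mindfulness" and runs on to the word preceded without a main clause to carry it.

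The only time term named for the multilevel model is a linear one: the aim is "to examine linear change over time as a fixed effect".

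Three other places bear on the point:

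- Item 6b lists the two mindfulness questionnaires (FFMQ and MPQ) as mediating measures, but no mediation analysis is given anywhere.
- The one model that uses individual change scores (Aim 2 Analyses) predicts post-training AUCI for cortisol. Cortisol is not among the ten outcomes in the precedence sentence, and the changes are not described as lagged.
- Neither hypothesis concerns order. The first is that "MBRT will improve self-reported measures over the 2.5-day intensive intervention" relative to baseline. The second is that changes "would predict post-MBRT salivary cortisol, while controlling for pre-MBRT salivary cortisol".

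**The concern.** A claim that one change preceded another needs an analysis that compares timing or, for a claim about process, one that links a person's earlier change to the same person's later change. The plan has neither. It tests each variable's mean change separately and gives no rule for turning five results per variable into a statement about order.

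At stake is the interpretation. With the analysis labelled in advance as a test, a report could present a table of significant and non-significant changes as evidence that mindfulness or emotion regulation moved first and the outcomes followed. The method does not examine that.

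**Working it through.** **Inputs from the documents.** There are four assessments (times 0 to 3), one group, and alpha .05 (two-sided assumed, since sidedness is not stated). The sample size is 2 cohorts × 35 = 70 anticipated (Sample Size), "for a minimum of 50 participants" (Design item 1). There are 3 process variables and 10 outcomes, so 3 × 10 = 30 pairs. The documents give no effect sizes, SDs or correlations, so every such value below is an assumption. Paired t-tests on complete data stand in for the mixed-model contrasts.

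**Structure first.**

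- Writing Y for an outcome, Y2 − Y0 = (Y1 − Y0) + (Y2 − Y1). If the outcome steps up by δ at time 1 and then stays flat, the expected 0–2 and 0–3 changes are both δ although nothing moved after time 1. Those two contrasts cannot show later movement.
- With a single linear slope b, the change over an interval of length L is b × L. Its test statistic is the same for every interval, so all intervals are significant or none is. Interval-specific results need time coded by occasion, which the plan does not state.

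**Does the list respond to a person-level link?** Let the process mean move only over 0–1 and the outcome mean only over 1–2, each by 0.5 SD of change. Let ρ be the correlation between a person's 0–1 process change and 1–2 outcome change. The process-first pattern is: process significant at 0–1, outcome not significant at 0–1, outcome significant at 1–2. There were 4,000 simulated trials per setting.

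| n | ρ | Pattern appears | Person-level lagged correlation significant |
|---|---|---|---|
| 50 | 0 | 83% | 5% |
| 50 | +0.5 | 84% | 96% |
| 50 | −0.5 | 83% | 97% |
| 70 | 0 | 92% | 5% |
| 70 | +0.5 | 93% | 99% |
| 70 | −0.5 | 93% | over 99% |

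The first row can be checked by hand from its component rates: 0.933 × (1 − 0.044) × 0.926 = 0.826. With ρ = 0.5 but no mean change at all, the pattern appears in about 1% of trials, while the lagged test rejects in 97% (n=50) and 99% (n=70).

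A second set-up had a process step of 0.3 or 0.5 SD at time 1, an outcome step of 0.3 SD at time 2, and a person-level SD of steps of 0.3 or 0.5. It compared step correlations of 0 and 0.9. Pattern rates included 27.0% v 29.6% (n=50) and 45.6% v 47.6% (n=70). The largest gap over eight settings was 29.6 − 27.0 = 2.6 points. With retest correlation 0.6 and same-occasion noise correlated 0.3, the largest gap was about 4.0 points (26.5% v 30.5%, n=50).

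**Does it describe group order safely?** Let both variables step up together at time 1 and stay up (outcome 0.3 SD, retest correlation 0.6, between-variable correlation 0.3; 20,000 replicates). Any process-first pattern is then false.

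| Counted as later | n | Process 0.3 SD | 0.4 SD | 0.5 SD |
|---|---|---|---|---|
| 1–2 and 2–3 only | 50 | 1.4% | 2.3% | 2.6% |
| 1–2 and 2–3 only | 70 | 1.5% | 2.0% | 2.2% |
| also 0–2 and 0–3 | 50 | 12.4% | 18.6% | 21.1% |
| also 0–2 and 0–3 | 70 | 10.8% | 14.4% | 16.0% |

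Over retest correlations 0.4 to 0.8 and between-variable correlations 0 to 0.6, the ranges are 0.3% to 3.3% and 1.9% to 22.9%.

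The low rates belong to a step followed by no change. If both variables instead improve by the same 0.3 SD of change over 0–1 and again over 1–2 (independent changes), the false pattern appears in 13% (n=50) and 15% (n=70), counting only 1–2 as later. Hand check at n=70: 0.700 × (1 − 0.698) × 0.703 = 0.149.

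**The case against.** The strongest reply is that the plan never says within-person. It says only that process changes preceded outcome changes. Read as a statement about group means, asking which variables move over 0–1 and which over 1–2 or 2–3 is a crude but recognisable look at order. On that reading, with only the later intervals counted, simultaneous steps give a false pattern in 1.4% to 2.6% of pairs, below alpha. The 0–2 and 0–3 contrasts have their own use, since the first hypothesis is improvement relative to baseline, and no text says they count as evidence of later movement. It can also be said that this is a single-group pilot, and that an exploratory lagged model would keep the question alive without new data.

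Much of this stands. The 11% to 21% rates are conditional on a reading the plan does not state, the harm is limited, and a lagged model is a legitimate alternative. The central point survives. Even for group means, a significant change in one variable beside a non-significant change in another is not a test that their timing differs. The plan gives no reading rule that would exclude the overlapping contrasts, and under gradual identical change the later-only reading still errs in 13% to 15% of pairs.

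**Conclusion.** The concern holds. The plan promises a test of precedence and specifies none; the listed analysis can at most describe when group means change. That rests on the structure of the analysis. The simulations only illustrate it, and their rates depend on assumed effects and correlations. Across the set-ups tried, moving the person-level link from none to strong shifted the pattern rate by no more than about 4 percentage points. False process-first patterns under simultaneous or identical change ranged from under 3% to about 21% in the main settings, according to the trajectory and which intervals count as later.

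Severity is minor: the aims and both hypotheses can be addressed without this analysis.

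**What to change.** In Design item 1 and in item 6d, Aim 1 Analyses, replace the sentence that announces the test with wording such as:

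> Changes in each process and outcome variable over 0–1, 1–2, 2–3, 0–2 and 0–3 will be estimated with 95% CIs, with time entered as a four-level factor, to describe the timing of group-mean change. No conclusion about precedence or mechanism will be drawn.

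Rewrite the broken sentence that opens item 6d to match.

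The cost is a text change and one line of model specification, with no new visits, data or participants. The study gives up a statement that its method could not support. The estimates will be fairly wide. The standardised half-width is t(.975, n−1) × √(2(1−r)) / √n. At an assumed retest correlation r = 0.6 this is 2.01 × 0.894 / 7.07 = 0.25 SD at n=50 and 1.99 × 0.894 / 8.37 = 0.21 SD at n=70. For r from 0.8 to 0.4 it runs from 0.18 to 0.31 SD and from 0.15 to 0.26 SD.

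If the sponsor wants to keep the question of order, the alternative is to prespecify an exploratory person-level model, for example 0–1 process change predicting 1–2 outcome change, adjusted for the earlier outcome level. By Fisher's z with complete data, a simple lagged correlation has 80% power at r of about 0.39 (n=50) or 0.33 (n=70). At r = 0.3, power is 56% and 72%.

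### The only test of Hypothesis 2 uses AUCI, the rise in cortisol after waking, so it can miss or reverse an association with cortisol level

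*Combined protocol and SAP*

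**What the plan says.** Hypothesis 2 (Hypotheses, second item) is that pre-to-post changes in mindfulness, physical health, mental health and stress "would predict post-MBRT salivary cortisol, while controlling for pre-MBRT salivary cortisol". It predicts an association and states no direction of cortisol change.

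The analysis appears under Design, item 1, and again under Design, item 6d, Aim 2 Analyses. It has two parts:

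- A REML multilevel model of the cortisol values, with phase of measurement, time after waking and their interaction.
- An association analysis based on AUCI, introduced as a way to study "the linear relationship between each independent variable and cortisol awakening levels". Here "Cortisol levels will be transformed into a single value by calculating the AUCI for each assessment day". Pre-AUCI enters in step 1, followed by "change in stress, physical health, mental health, and mindfulness entered in step 2, to predict post-AUCI".

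No level summary, such as the area with respect to ground (AUCG) or the mean of the three samples, is planned for the regression. Separately, Specific aim #1 and the overall goal under Process Evaluation speak of "reduced stress as measured by salivary cortisol". Nothing says which cortisol contrast, or which sign, would count as that reduction.

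**The concern.** The hypothesis and the description of the regression both speak of cortisol or cortisol levels, but the variable analysed is the rise above the waking value. These are different quantities. If participants whose mindfulness improves most also have the largest fall in cortisol output, the regression may show no association, or one with the opposite sign. A report that follows the plan's wording would then state a conclusion about salivary cortisol from a variable that does not contain its level. Since no direction of benefit is given for AUCI, either sign could afterwards be presented as favourable.

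**Working it through.** **Inputs.** Sampling times of 0, 30 and 45 minutes, and an expected rise of 50 to 75% within 30 minutes, come from Design, item 6b, Secondary Outcome Measures. The documents give no AUCI formula, cortisol values or SDs. The standard trapezoid definition and all profiles below are therefore assumptions, in arbitrary units. The plan has no figure of its own to reproduce on this point.

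**Formulas.**

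AUCG = 30(c0 + c30)/2 + 15(c30 + c45)/2 = 15·c0 + 22.5·c30 + 7.5·c45

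AUCI = AUCG - 45·c0 = -30·c0 + 22.5·c30 + 7.5·c45

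The AUCI weights sum to -30 + 22.5 + 7.5 = 0, so an equal shift in all three samples cancels exactly. If the samples fall by d0, d30 and d45, AUCI changes by 30·[d0 - (0.75·d30 + 0.25·d45)]. It rises when the waking fall exceeds the weighted later fall, stays flat when they are equal, and falls otherwise. This is algebra and depends on no assumed SD.

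**Illustrations.**

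| Before | After | Pattern | AUCG | AUCI |
|---|---|---|---|---|
| 10/16/14 | 6/12/10 | equal fall of 4 | 615 to 435 (-29%) | 165 to 165 |
| 10/16/14 | 6/16/14 | waking sample only | 615 to 555 (-10%) | 165 to 285 (+73%) |
| 10/16/14 | 6/9.6/8.4 | 40% fall throughout | 615 to 369 (-40%) | 165 to 99 (-40%) |
| 10/16/16 | 6/14/14 | falls of 4/2/2 | 630 to 510 (-19%) | 180 to 240 (+33%) |
| 10/15/15 | 7/12/12 | equal fall of 3 | 600 to 465 (-22.5%) | 150 to 150 |
| 10/15/15 | 8.4/14.7/14.7 | falls of 1.6/0.3/0.3 | 600 to 567 (-5.5%) | 150 to 189 (+26%) |

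In the last two rows the rise at 30 minutes stays within the documents' 50 to 75% on both days: 50% before, then 5/7 = 71% and 6.3/8.4 = 75% after.

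**Consequence for the regression.** Suppose each unit of improvement in a predictor goes with falls of 4/2/2, and pre-training values are unrelated to improvement. The slope is -(15×4 + 22.5×2 + 7.5×2) = -120 for post-AUCG, and 30×(4 - 2) = +60 for post-AUCI. With equal falls of 3 per unit, the slopes are -(45×3) = -135 and 0. Pre-AUCI in step 1 does not repair this, because it omits level too. For the same reason it does not adjust for the pre-training cortisol level.

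**The multilevel model.** A simulation (2,000 runs, two-sided 0.05, assumed SDs of 3 between persons, 2 between days and 2 between samples) used a paired test of the day mean in place of the phase effect. For a uniform fall of 2 units, that test rejected in 99% of runs at N = 50 and 99.9% at N = 70. A paired test of AUCI rejected in 5.7% and 4.5%, about the type I error rate. The planned model can therefore show a group fall in level. Its terms are only phase, time after waking and their interaction, so it says nothing on whether changes in mindfulness, stress or health predict cortisol.

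**The case against.** A reader might infer that the plan cannot show reduced stress by cortisol at all. The documents do not support that. The reduced-stress statement belongs to Specific aim #1 and the overall goal, not to Hypothesis 2, and the phase effect in the multilevel model uses the cortisol values themselves.

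A reader might also infer that AUCI is the wrong measure and should give way to AUCG, with lower values counted as benefit. That does not follow either. The plan introduces cortisol largely through the awakening response, which it describes as a sharp rise, and AUCI is a legitimate measure of a rise. The literature review (Design, item 12) says the measures will be identical to those of the earlier police pilot. Whether that covers AUCI cannot be checked here, but it is a reason to keep it. The documents never mention AUCG or say that a lower value is better.

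The illustrations can be called selective. Under a proportional fall, AUCI falls with the level, and the after-profiles in the first, second and fourth rows rise by 100%, 167% and 133%, beyond the documents' range. The first part stands: the sign depends on the pattern. The second does not remove the problem, because the last two rows stay within the range and still leave AUCI flat or raise it.

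Finally, cortisol is a secondary outcome in a pilot, and rewording Hypothesis 2 to the awakening rise would cure the mismatch. That is true, but the regression would then say nothing about cortisol level.

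**Conclusion.** The concern holds for the Hypothesis 2 regression and for its description. As planned, that regression tests an association with the awakening rise. It can miss an association with cortisol level completely, or reverse its sign, and the statement that it relates predictors to cortisol awakening levels is wrong. The blindness to a uniform shift is exact under the standard AUCI definition. How far AUCI and level would diverge in these participants is unknown, since the documents give no cortisol data.

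The Aim 1 statement can be addressed at group level through the phase effect, but the plan names neither the contrast nor its direction. With the interaction in the model, the phase effect is an average change in level only under centred coding of time after waking. Under reference coding it is the change at the reference sample, and the coding is not stated. The point does not touch the self-report primary outcomes. It is worth correcting because cortisol is the only biological measure and has its own hypothesis.

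**What to change.** In Aim 2 Analyses, and in the matching text under Design, item 1:

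- Run the same hierarchical regression also with a level summary (AUCG or the mean of the same three samples), with its pre-training value in step 1, beside the AUCI regression. Name in advance which summary is the main test of Hypothesis 2.
- Where AUCI is meant, replace the reference to cortisol awakening levels with awakening rise.
- Name the phase contrast for level, averaged over the three samples, as the basis for the reduced-stress statement in Specific aim #1. State its direction and which assessment times it compares, because saliva is planned at four.
- State that neither sign of AUCI will be read as benefit.

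The cost is one derived variable from samples already planned and a few sentences of text. There is no new saliva and no change to procedures. The downside is a second cortisol summary to report and one more test, which is why the main one must be named beforehand.
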